8.3.9 Guidelines for reporting product complaints

Please refer to the master protocol.

8.4 PHARMACOKINETICS

Please refer to the master protocol.

8.5 PHARMACODYNAMICS

Please refer to the master protocol.

8.6 GENETICS AND/OR PHARMACOGENOMICS

Please refer to the master protocol.

8.7 BIOMARKERS

Please refer to the master protocol.

8.8 IMMUNOGENICITY ASSESSMENTS

Please refer to the master protocol.

8.9 HEALTH ECONOMICS

Please refer to the master protocol.

Amended Clinical Trial Protocol 01 (Substudy 01) 28-Apr-2022
SAR444245-ACT16941 Version number: 1

8.10 USE OF BIOLOGICAL SAMPLES AND DATA FOR FUTURE RESEARCH

Please refer to the master protocol.

9 STATISTICAL CONSIDERATIONS

9.1 STATISTICAL HYPOTHESES

Please refer to the master protocol.

9.2 SAMPLE SIZE DETERMINATION

The study will start with a safety run-in with 6-10 participants from Cohort A. Participants who are enrolled in the safety run-in and treated at the confirmed safe dose will be included in the total number of participants in Cohort A.

Sample size:

The plan is to treat a total of 25 participants at the confirmed safe dose in Cohort A.

Table 9 lists estimated CRR and the corresponding 90% exact confidence interval (CI) by number of responders from a sample size of 25 participants in Cohort A.

Table 9 - Cohort A: Estimated complete response rate (CRR) depending on number of responders

Number of Responders (N=25)	Complete Response Rate in % (90% Clopper-Pearson CI)
1	4 % (0.2% - 17.6%)
3	12 % (3.4% - 28.2%)
4	16 % (5.7% - 33%)
5	20 % (8.2% - 37.5%)
6	24 % (11% - 42%)
8	32 % (17% - 50.4%)
9	36 % (20.2% - 54.4%)

With a sample size of 25 participants in Cohorts A, the probability of observing 1 or more instances of a specific AE with a true incidence rate of 1%, 2% or 5% is 22.2%, 39.7% or 72.3% respectively.

This provides reasonable assurance that events occurring at $\geq 5\%$ frequency can be identified in this substudy.

9.3 POPULATIONS FOR ANALYSES

Please refer to the master protocol.

9.4 STATISTICAL ANALYSES

Please refer to the master protocol.

9.4.1 General considerations

Please refer to the master protocol.

9.4.2 Primary endpoint(s)

For Cohort A, the complete response rate (CRR) is defined as the proportion of participants who have a CR per Investigator assessment (Lugano response criteria 2014).

The BOR is the best overall response observed from the date of first IMP until disease progression, death, cut-off date or initiation of post-treatment anticancer therapy, whichever occurs first. The BOR will be summarized with descriptive statistics.

The CRR and the BOR will be summarized with descriptive statistics. In addition, two-sided 90% CIs will be computed for CRR from Clopper-Pearson exact method.

9.4.3 Secondary endpoint(s)

Please refer to the master protocol for descriptions of common secondary endpoints. Substudy-specific analysis for secondary endpoints is summarized below.

9.4.3.1 *Objective response rate*

The ORR is defined as the proportion of participants who have a CR or partial response (PR) per Investigator assessment (Lugano response criteria 2014).

The ORR will be summarized with descriptive statistics and the corresponding two-sided 90% CIs calculated from Clopper Pearson exact method will be also presented.

9.5 INTERIM ANALYSES

Please refer to the master protocol.

The cohort cut-off for the primary endpoint analysis is estimated to be approximately 8 months from the date of the last participant's first infusion. This would allow the possibility to observe the response of the last participant for 6 months, assuming there is a response at first treatment assessment.

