The initial tumor imaging FDG-PET CT and/or MRI will be performed within 28 days prior to C1D1. Scans performed as part of routine clinical management are acceptable for use as the screening scan if they are of diagnostic quality and performed within 28 days prior to the date of enrollment. On study imaging will be performed every 9 weeks (63 ± 7 days) after the date of first IMP and if clinically indicated. FDG-PET must be performed for the 9-week and 18-week on-treatment assessments. Imaging studies should follow calendar days and should not be adjusted for delays in cycle starts or extension. The same imaging technique should be used in a participant throughout the trial. After Week 45 tumor imaging should be performed every 12 weeks (84 ± 7 days) until progressive disease (PD). Brain CT/MRI will be performed if clinically indicated.

PET imaging is always required to confirm the first documented complete response (CR). If the first documented radiological CR is seen on CT scan only, a confirmatory PET scan (either FDG PET or PET-CT) should be obtained within 14 days to confirm that timepoint's response of CR. If the PET scan is not obtained within 14 days, the timepoint must be assessed as a PR, and the next scan should be done by one of the 3 methods above as soon as possible to confirm the CR. Once CR has been established by PET imaging, subsequent CR and/or PD may be followed by CT imaging only. The CT component of the PET-CT may be used in lieu of a standalone CT/MRI, only if the CT component is of similar diagnostic quality as a contrast enhanced CT performed without PET. If contrast enhanced PET-CT with diagnostic CT is not available, a standard FDG-PET must be performed, and a standalone diagnostic CT/MRI should be performed in addition to the FDG-PET scan. If independent CT and PET scanners are used, and the participant is receiving both scans on the same day, the PET must be performed prior to the CT with IV contrast so as to not compromise PET results. The PET-CT acquisition methodology (eg, administration of intravenous contrast) should remain consistent at all imaging visits for any given patient.

Bone marrow sample is mandated to confirm CR if bone marrow was involved by lymphoma or involvement is unknown prior to study treatment and as “clinically indicated” and “If bone marrow biopsy is not negative, a radiographic timepoint response (TPR) of CR at that time point would be downgraded to an overall PR”.

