3 STATISTICAL ANALYSES

3.1 GENERAL CONSIDERATIONS

In general, continuous data will be summarized using the number of observations available, mean, standard deviation (SD), median, minimum, and maximum. Categorical and ordinal data will be summarized using the count and percentage of participants.

The baseline value is defined as the last available value before the first administration of any of the two IMPs (SAR444245 or pembrolizumab). For participants enrolled but not treated, the baseline value is defined as the last available value before enrollment.

Unless otherwise specified, analyses will be performed by cohort, by dose level (if applicable) and overall. Participants enrolled in the safety run-in part and treated at the RP2D will be included in the analyses of the core part.

All efficacy analyses will be performed on the efficacy population. Complete response rate (CRR, for cohort A) and objective response rate (ORR, for cohort C1), as well as all other response-related efficacy endpoints will be derived using the Investigator's assessment per Lugano response criteria 2014 for all cohorts.

All safety analyses will be performed on the exposed population.

Central imaging may be done retrospectively if significant activity is observed (See [Section 3.2.3](#) for sensitivity analysis).

Confidence intervals will be two-sided 90% CI for efficacy analyses. CI will be used for descriptive purposes only, without inference.

The BOR is defined as the best overall response observed from the date of first IMP until disease progression, death, cut-off date or initiation of subsequent anti-cancer therapy, whichever occurs first.

Analysis period

The analysis period will be divided into 3 segments:

- The **pre-treatment period** is defined as the time from when the participants give informed consent to the first administration of the IMP.
- The **on-treatment period** (i.e., treatment-emergent (TE) period) is defined as the time from the first administration of IMP up to 30 days after the last administration of IMP.
- The **post-treatment period** is defined as the time from the end of the on-treatment, ie. 31 days after the last administration of IMP.

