3.8 INTERIM ANALYSES

No formal interim analyses are planned. However, at the end of the safety run-in of each cohort, the occurrence of DLTs and other safety data will be reviewed by the Study Board (SB) to decide about continuation of the dose of SAR444245 24 µg/kg or reduced to [REDACTED] µg/kg or another lower dose level.

In addition, the cumulative safety data for each study intervention across cohorts will be reviewed periodically by the independent Data Monitoring Committee (DMC). The enrollment will not be paused or stopped during the safety monitoring unless severe safety concern arises. DMC will review safety data periodically. Ad hoc DMC meetings may also be held if a significant safety issue or an issue deemed important for discussion arises on this or other SAR444245 studies. Occurrence of any treatment related Grade 3 or higher AE (excluding lymphocyte count decrease) not resolving within 72 hours in >25% of participants will trigger ad hoc DMC. The DMC procedures will be detailed in the DMC charter and approved by the DMC members.

In addition, for each cohort, in order to support project strategic planning and design of future studies, informal interim analysis(es) may be conducted during the core phase part of the study, e.g., after 12 participants have undergone at least 1 post-baseline tumor assessments or have discontinued the study intervention, whichever is earlier.

The cohort cut-off for the primary endpoint analysis is estimated to be approximately 8 months from the date of the last participant's first infusion.

For each cohort, the cut-off date for the final analysis (i.e., analysis of secondary objectives and update of primary objective) will be 3 years from cohort LPI.

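### Should the primary cut-off of about 8 months be tied to the last participant's Week 36 scan?

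*Protocol*

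**What the plan says.** Substudy 01 (Cohort A) and Substudy 03 (Cohort C1) use the same text in section 9.5: "The cohort cut-off for the primary endpoint analysis is estimated to be approximately 8 months" counted from the last participant's first infusion. The reason given is "This would allow the possibility to observe the response of the last participant for 6 months", on the assumption that the response is seen at the first on-treatment assessment. SAP 3.8 states that the cut-off "is estimated to be approximately 8 months from the date of the last" participant's first infusion. It gives no reason and names no visit.

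The cut-off date is part of the endpoint. In section 9.4.2 of both substudies, best overall response is counted from first dose "until disease progression, death, cut-off date or initiation of post-treatment anticancer therapy, whichever occurs first". SAP 3.1 has the same rule: "until disease progression, death, cut-off date or initiation of subsequent anti-cancer therapy, whichever occurs first". Complete response rate (CRR, primary in Cohort A) and objective response rate (ORR, primary in Cohort C1) are read from best overall response.

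The scan calendar is in master protocol 8.1.1: "On study imaging will be performed every 9 weeks" (63 ± 7 days from first dose), moving to every 12 weeks only after Week 45. It adds: "Imaging studies should follow calendar days and should not be adjusted for delays in cycle starts or extension". Master protocol 4.1 and SAP 3.8 place the final analysis 3 years after the cohort's last participant enters. That analysis covers the secondary objectives and updates the primary one.

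**The concern.** Response is observed by scan, and the stated purpose of the 8 months is 6 months of response observation. If the cut is placed at exactly 8.0 months, it falls just ahead of the Week 36 assessment. The last enrollees' scheduled imaging would then usually end at Week 27, and a Week 9 response would be documented by scheduled scan for only about 4 months.

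Because best overall response stops at the cut-off date, whether those participants' Week 36 scans count depends on how the word approximately is read. The trial is open-label, uncontrolled and investigator-assessed, and one response among 25 participants is 4 percentage points. A cut-off left open by a week or two can therefore look like a judgement made with results in view.

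**Working it through.** **Inputs**
- Cut-off: about 8 months from the last participant's first infusion (section 9.5 of each substudy; SAP 3.8).
- Month length: 30.4375 days, the SAP's exposure convention (SAP 3.6.1.1).
- Scans: Week 9 = day 63 (56 to 70), Week 18 = day 126, Week 27 = day 189, Week 36 = day 252 (245 to 259) (master protocol 8.1.1).

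**The plan's own figure**
- 8 × 30.4375 = 243.5 days.
- After a nominal Week 9 scan: 243.5 − 63 = 180.5 days; 180.5 / 30.4375 = 5.93 months.
- First scan at day 70: 173.5 days = 5.70 months. First scan at day 56: 187.5 days = 6.16 months.

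The stated 6 months is reproduced as calendar follow-up.

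**Position against the Week 36 scan**
- Window opens: 245 / 30.4375 = 8.05 months, which is 245 − 243.5 = 1.5 days after 8.0 months.
- Nominal date: 252 / 30.4375 = 8.28 months, 8.5 days after.
- Window closes: 259 / 30.4375 = 8.51 months, 15.5 days after.
- Eight true calendar months last 242 to 245 days, so a literal reading reaches at most the first day of the window.
- A figure rounded to 8 months spans 7.5 to 8.5 months, or 228.3 to 258.7 days. That range contains day 252.

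**Scan-to-scan follow-up of a Week 9 response**

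| Last scan counted | Days from Week 9 | Months |
|---|---|---|
| Week 27 (nominal) | 189 − 63 = 126 | 4.14 |
| Week 36 (nominal) | 252 − 63 = 189 | 6.21 |
| Week 36, shortest within both windows | 245 − 70 = 175 | 5.7 |
| Week 36, longest within both windows | 259 − 56 = 203 | 6.7 |

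Tying the cut to Week 36 gives 5.7 to 6.7 months by scan. Its lower end is the same as that of the present calendar follow-up (5.7 to 6.2 months).

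**Participants concerned**

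Only those first dosed shortly before the last participant matter. The documents give no accrual rate, so I assume r = 1 to 4 participants per month.
- Nominal Week 36 date: 1 + r × 8.5 / 30.4375 = 1.28 to 2.12 of 25.
- End of window: 1 + r × 15.5 / 30.4375 = 1.51 to 3.04 of 25.

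These are upper counts. Best overall response has already ended for anyone who progressed, died or started another therapy. Participants off treatment without progression are imaged every 3 months from their last dose (master protocol 4.1), so they may have no Week 36 scan.

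**Size of one changed response**

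From the substudies' own sample-size tables, 5 of 25 is 20% (90% CI 8.2% to 37.5%) and 6 of 25 is 24% (11% to 42%). A shift of one response is small beside either interval. A later cut can only leave the number of responders unchanged or raise it, since best response cannot get worse with more follow-up.

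**The case for a change.** The best argument for acting is that it costs almost nothing. A cut 15.5 days later, or one sentence per section, would settle whether Week 36 counts and bring the cut-off into line with its stated purpose. In an open-label trial there is value in fixing the data cut in advance. It is true that no passage says whether the last participant's Week 36 scan is included, and that part of the objection stands.

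The rest is weaker.
- The 6 months describes an opportunity to observe. It is not an endpoint and is not said to run from scan to scan. Where 6 months does define an endpoint, in clinical benefit rate, the plan ties it to an assessment: 26 weeks, allowing for the window of the Week 27 scan (master protocol 9.4.3.3, SAP 3.3.1.1).
- Naming Week 36 would not guarantee 6 months by scan, given the 5.7-month lower end above.
- It would not close every loose end either. Participants imaged every 3 months off treatment need their own provision.
- A first complete response seen on CT alone still needs PET: "If the PET scan is not obtained within 14 days, the timepoint must be assessed as a PR". FDG-PET is mandatory on treatment only at Weeks 9 and 18, so a CT-only response at day 259 could remain open to day 273 (8.97 months). Bone marrow confirmation, where required, has a 14-day allowance too (master protocol 8.1.1, Table 4).

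**Conclusion.** No change to the plan is needed. The cut-off is worded as an approximate estimate, its stated 6 months is correct as calendar follow-up (5.9 months; 5.7 to 6.2 across the Week 9 window), and the Week 36 scan at 8.28 months fits within it. Whether that scan is in the primary cut is a detail that the team settles when it sets the data-cut date.

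Either choice gives a sound estimate. CRR and ORR require no minimum duration, the intervals are descriptive, and no hypothesis is tested. Duration of response, as a secondary endpoint, belongs to the 3-year analysis, where any first response at Week 36 would also enter the updated primary result.

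The possible effect is confined to a first response, or first complete response, at Week 36 in at most about 1 to 3 of 25 participants per cohort. That count rests on the assumed accrual of 1 to 4 per month; faster accrual would raise it. No effect on CRR or ORR has been shown. A sentence saying whether Week 36 is included would be a drafting nicety and would correct no result.

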10 SUPPORTING DOCUMENTATION AND OPERATIONAL CONSIDERATIONS

10.1 APPENDIX 1: REGULATORY, ETHICAL, AND STUDY OVERSIGHT CONSIDERATIONS

10.1.1 Regulatory and ethical considerations

Please refer to the master protocol.

10.1.2 Financial disclosure

Please refer to the master protocol.

10.1.3 Informed consent process

Please refer to the master protocol.

10.1.4 Data protection

Please refer to the master protocol.

10.1.5 Committees structure

Please refer to the master protocol.

10.1.6 Dissemination of clinical study data

Please refer to the master protocol.

Study participants results summaries will be provided in any one of the clinical trial portals after completion of the substudy, until the end of study.

10.1.7 Data quality assurance

Please refer to the master protocol.

10.1.8 Source documents

Please refer to the master protocol.

10.1.9 Study and site start and closure

Please refer to the master protocol.

10.1.10 Publication policy

Please refer to the master protocol.

10.2 APPENDIX 2: CLINICAL LABORATORY TESTS

Please refer to the master protocol.

10.3 APPENDIX 3: AES AND SAES: DEFINITIONS AND PROCEDURES FOR RECORDING, EVALUATING, FOLLOW-UP, AND REPORTING

Please refer to the master protocol.

10.4 APPENDIX 4: CONTRACEPTIVE AND BARRIER GUIDANCE

Please refer to the master protocol.

10.5 APPENDIX 5: GENETICS

Please refer to the master protocol.

10.6 APPENDIX 6: LIVER AND OTHER SAFETY: SUGGESTED ACTIONS AND FOLLOW-UP ASSESSMENTS

Please refer to the master protocol.

10.7 APPENDIX 7: COUNTRY-SPECIFIC REQUIREMENTS

Please refer to the master protocol, and in addition to the requirements listed in the master protocol:

France**Section 1.3 Schedule of Activities (SoA) (Section 1.3)**

In France, serology for HIV will be tested at screening.

10.8 APPENDIX 8: CRITERIA FOR RESPONSE ASSESSMENT

Please refer to the master protocol.

10.9 APPENDIX 9: CONTINGENCY MEASURES FOR A REGIONAL OR NATIONAL EMERGENCY THAT IS DECLARED BY A GOVERNMENTAL AGENCY

Please refer to the master protocol.

10.10 APPENDIX 10: RISK ASSESSMENT

Please refer to the master protocol for detailed information about SAR444245, available information about pembrolizumab is shown in [Table 10](#).

Table 10 - Risk assessment

Potential risk of clinical significance	Summary of data/rationale for risk	Mitigation strategy
Study intervention(s)		
Infusion-related reactions	Pembrolizumab Common, but infusion-related reactions in labeling include drug hypersensitivity, anaphylactic reaction, anaphylactoid reaction, hypersensitivity and cytokine release syndrome.	Pembrolizumab Dose modification and treatment guidelines for pembrolizumab infusion-related reactions are provided in Table 3 .
Hypersensitivity, including anaphylaxis	Pembrolizumab Not specifically reported, but included among infusion-related reactions in label.	Exclusion of participants with known hypersensitivity to any components of pembrolizumab.
Infections	Pembrolizumab Common: pneumonia.	See routine mitigation in the master protocol.
Hepatotoxicity	Pembrolizumab Hepatitis occurred in 1.0% of patients, including Grade 2, 3 or 4 cases in 0.1%, 0.7% and 0.1% patients, respectively, receiving pembrolizumab. The median time to onset of hepatitis was 3.8 months (range 8 days to 26.3 months). The median duration was 1.1 months (range 1 day to 20.9+ months). Hepatitis led to discontinuation of pembrolizumab in 0.4% patients. Hepatitis resolved in 46 patients.	Dose modification and treatment guidelines for liver enzyme increase are provided under immune-related reactions in Table 6 .
Nephrotoxicity	Pembrolizumab Common: nephritis, acute kidney injury.	Dose modification and treatment guidelines for nephrotoxicity are provided under immune-related reactions in Table 6 .
Neurological AEs	Pembrolizumab Dizziness, headache, neuropathy peripheral, dysgeusia (very common) and lethargy (common) for pembrolizumab in combination with chemotherapy. Uncommon: epilepsy.	Dose modification and treatment guidelines for neurological AEs are provided under immune-related reactions in Table 6 .
Immune-mediated Adverse Events	Pembrolizumab Immune-mediated adverse events are designated as important identified risk for pembrolizumab.	Dose modification and treatment guidelines for immune-related reactions are provided in Table 6 .
Risks related to special populations		
Pregnancy and lactation exposure and outcomes	Pembrolizumab Pembrolizumab should not be used during pregnancy unless the clinical condition of the woman requires treatment with pembrolizumab.	See master protocol for exclusion of participants, guidance on highly effective contraceptive methods, and pregnancy tests to be performed regularly.
Drug-drug interactions	No data available.	

Potential risk of clinical significance	Summary of data/rationale for risk	Mitigation strategy
Overdose and its treatment	No specific information is available on the treatment of overdose of pembrolizumab.	See Section 6.7

10.11 APPENDIX 11: ASTCT ASSESSMENT FOR ICANS AND CRS

Please refer to the master protocol.

10.12 APPENDIX 12: GUIDELINES FOR THE MANAGEMENT OF TUMOR LYSIS SYNDROME (TLS)

Please refer to the master protocol.

10.13 APPENDIX 13: ECOG PERFORMANCE STATUS AND LANSKY SCALE

Please refer to the master protocol.

10.14 APPENDIX 14: ABBREVIATIONS

AE:	adverse event
ASCT:	autologous stem cell transplantation
BOR:	best overall response
cHL:	classic Hodgkin lymphoma
COVID-19:	Corona Virus Disease 2019
CR:	complete response
CRF:	case report form
CRS:	cytokine-release syndrome
CTLA-4:	cytotoxic T-lymphocyte-associated protein 4
DLT:	dose-limiting toxicity
ICANS:	immune cell-associated neurotoxicity syndrome
IL-2:	interleukin 2
IMP:	investigational medicinal product
irAE:	immune-related adverse event
IRR:	infusion-related reaction
IV:	intravenous
NHP:	non-human primate
ORR:	objective response rate
PD1:	programmed cell death protein 1
PD-L1:	programmed cell death-ligand 1
PR:	partial response

Amended Clinical Trial Protocol 01 (Substudy 01) 28-Apr-2022
SAR444245-ACT16941 Version number: 1

Q3W: every 3 weeks
TIL: tumor-infiltrating lymphocyte
TRAE: treatment-related adverse event
VLS: vascular leak syndrome

10.15 APPENDIX 15: PROTOCOL AMENDMENT HISTORY

The Protocol Amendment Summary of Changes Table for the current amendment is located directly before the Table of Contents (TOC).

